2.5.3 Handling of missing values/censoring/discontinuations

Missing data for ASAS40 response for data up to Week 16 will be handled as follows:

1. Participants who discontinue from treatment or study for any reason will be considered as non-responders from the time of discontinuation through Week 16
2. Participants who do not have the required data to compute responses (i.e., ASAS components) at BSL and at the specific timepoint will be classified as non-responders at the specific timepoint.

Participants who are unblinded prior to the scheduled time point will be considered non-responders from the time of unblinding up to Week 16.

The primary analysis will use the non-responder imputation.

2.6 Analysis of the secondary objective

2.6.1 Secondary endpoint

The secondary efficacy variables are described below. Secondary efficacy variables will be analyzed using the FAS population.

- ASAS40 at Week 16
- ASAS 5/6 at Week16
- BASDAI at Week 16
- BASDAI50 at Week 16
- hsCRP at Week 16
- BASFI at Week 16
- SI joint edema on MRI at Week 16
- ASAS20 at Week 16
- SF-36 PCS at Week 16
- ASQoL at Week 16
- ASAS partial remission at Week 16

The clinical questions of interest are:

- What is the effect of secukinumab 150 mg s.c. versus placebo on the composite endpoint ASAS 40 response at Week 16 and the completion of 16 weeks-treatment in Chinese participants with active nr-axSpA?
- What is the effect of secukinumab 150 mg s.c. versus placebo on the composite endpoint ASAS 5/6 response at Week 16 and the completion of 16 weeks-treatment in Chinese participants with active nr-axSpA?
- What is the effect of secukinumab 150 mg s.c. versus placebo on the change from baseline in BASDAI at Week 16 in Chinese participants with active nr-axSpA had patients completed 16 weeks-treatment?
- What is the effect of secukinumab 150 mg s.c. versus placebo on the composite endpoint BASDAI 50 response at Week 16 and the completion of 16 weeks-treatment in Chinese participants with active nr-axSpA?
- What is the effect of secukinumab 150 mg s.c. versus placebo on the change from baseline in hsCRP at Week 16 in Chinese participants with active nr-axSpA had participants completed 16 weeks-treatment?
- What is the effect of secukinumab 150 mg s.c. versus placebo on the change from baseline in BASFI at Week 16 in Chinese participants with active nr-axSpA had patients completed 16 weeks-treatment?

- What is the effect of secukinumab 150 mg s.c. versus placebo on the change from baseline in SI joint edema on MRI at Week 16 in Chinese participants with active nr-axSpA had participants completed 16 week-treatment?
- What is the effect of secukinumab 150 mg s.c. versus placebo on the composite endpoint ASAS20 response at Week 16 and the completion of 16 weeks-treatment in Chinese participants with active nr-axSpA?
- What is the effect of secukinumab 150 mg s.c. versus placebo on the change from baseline in SF-36 PCS at Week 16 in Chinese participants with active nr-axSpA had participants completed 16 weeks-treatment?
- What is the effect of secukinumab 150 mg s.c. versus placebo on the change from baseline in ASQoL at Week 16 in Chinese participants with active nr-axSpA had participants completed 16 weeks-treatment?
- What is the effect of secukinumab 150 mg s.c. versus placebo on the composite endpoint ASAS partial remission response at Week 16 and the completion of 16 weeks-treatment in Chinese participants with active nr-axSpA?

The justification for targeting this treatment effect is that we wish to estimate the effect of the study drug for the full duration when administered without dose changes.

The estimand definition of all secondary binary variables (e.g., ASAS 5/6, etc.) will have the same attributes as that for the primary estimand, except for the variable of interest.

Estimand definition for the secondary continuous variables (e.g., BASDAI change from baseline, etc.) is the following:

- A. Population: defined through appropriate inclusion/exclusion criteria to reflect the targeted nr-axSpA population
- B. Variable: change from baseline in the variable of interest
- C: Treatment of interest: Secukinumab 150 mg s.c and Placebo
- D. Intercurrent event: discontinuation from treatment or study prior to Week 16
- E. Population-level summary: difference in variable means between Secukinumab 150 mg and Placebo groups

2.6.2 Statistical hypothesis, model, and method of analysis

ASAS40 at Week 16

The proportion of patients meeting the response criteria will be evaluated using a logistic regression model with treatment group and stratification factor (CRP+/MRI+, CRP+/MRI-, CRP-/MRI+) as factors and weight as a covariate.

ASAS 5/6 at Week 16

The proportion of participants meeting the response criteria will be evaluated using a logistic regression model with treatment group and stratification factor (CRP+/MRI+, CRP+/MRI-, CRP-/MRI+) as factors and weight as a covariate.

BASDAI at Week 16

Between-treatment differences in the change from baseline in BASDAI will be evaluated using MMRM with treatment group, stratification factor (CRP+/MRI+, CRP+/MRI-, CRP-/MRI+) and analysis visit as factors and baseline BASDAI score and weight as continuous covariates. Treatment by analysis visit and baseline BASDAI score by analysis visit will be included as interaction terms in the model. An unstructured covariance structure will be assumed for the model.

BASDAI50 at Week 16

The proportion of participants meeting the response criteria at Week 16 will be evaluated using a logistic regression model with treatment group and stratification factor (CRP+/MRI+, CRP+/MRI-, CRP-/MRI+) as factors and baseline weight and baseline BASDAI score as covariates.

hsCRP at Week 16

For the change in hsCRP, since evidence from the literature would suggest that the data are not normally distributed (Huffman et al. 2006), analysis will be performed on the \log_e ratio of the treatment value vs baseline value (calculated by dividing the post-baseline value by the baseline value and then applying the \log_e transformation) to normalize the distribution of hsCRP at each analysis visit. Between-treatment differences in the change in hsCRP relative to baseline will be evaluated using MMRM with treatment group, stratification factor (CRP+/MRI+, CRP+/MRI-, CRP-/MRI+) and analysis visit as factors and \log_e baseline hsCRP and weight as continuous covariates. Treatment by analysis visit and \log_e baseline hsCRP by analysis visit will be included as interaction terms in the model. An unstructured covariance structure will be assumed for the model. The estimate and the 2-sided 95% confidence intervals obtained from the model will be back transformed to the original scale.

BASFI at Week 16

Between-treatment differences in the change from baseline in BASFI will be evaluated using MMRM with treatment group, stratification factor (CRP+/MRI+, CRP+/MRI-, CRP-/MRI+) and analysis visit as factors and baseline BASFI score and weight as continuous covariates. Treatment by analysis visit and baseline BASFI score by analysis visit will be included as interaction terms in the model. An unstructured covariance structure will be assumed for the model.

SI joint edema on MRI at Week 16

The change from baseline to Week 16 in inflammation measured by SI joint total edema score will be evaluated using an ANCOVA model with treatment group, stratification factor (CRP+/MRI+, CRP+/MRI-, CRP-/MRI+) as factors, and weight and baseline inflammation score as covariates. Missing data will be imputed using multiple imputation prior to running ANCOVA.

ASAS20 at Week 16

The proportion of participants meeting the response criteria will be evaluated using a logistic regression model with treatment group and stratification factor (CRP+/MRI+, CRP+/MRI-, CRP-/MRI+) as factors and weight as a covariate.

SF-36 PCS at Week 16

Between-treatment differences in the change from BSL in SF36-PCS summary score will be evaluated using a MMRM with treatment group, stratification factor (CRP+/MRI+, CRP+/MRI-, CRP-/MRI+) and analysis visit as factors and baseline SF-36 PCS score and weight as covariates. Treatment by analysis visit and baseline SF-36 PCS score by analysis visit will be included as interaction terms in the model. An unstructured covariance structure will be assumed for the model.

ASQoL at Week 16

Summary statistics of observed data by visit and change from baseline in ASQoL will be provided for each treatment regimen. Between-treatment differences will be evaluated using MMRM. Treatment group, stratification factor (CRP+/MRI+, CRP+/MRI-, CRP-/MRI+) and analysis visit will be included as categorical factors and baseline ASQoL scores and weight as continuous covariates. Treatment by analysis visit and baseline ASQoL scores by analysis visit will be included as interaction terms in the model. An unstructured covariance structure will be assumed for the model.

ASAS partial remission at Week 16

Response at Week 16 to ASAS partial remission criteria will be evaluated using a logistic regression model with treatment and stratification factor (CRP+/MRI+, CRP+/MRI-, CRP-/MRI+) as factors and weight as a covariate.

2.6.3 Handling of missing values/censoring/discontinuations

Missing data for binary efficacy variables (e.g., ASAS5/6, etc.) for data up to Week 16 will be handled as follows:

1. participants who discontinue from treatment or study for any reason will be considered as non-responders from the time of discontinuation through Week 16
2. participants who do not have the required data to compute responses (i.e., ASAS components) at BSL and at the specific timepoint will be classified as non-responders at the specific timepoint.

Participants who are unblinded prior to the scheduled time point will be considered non-responders from the time of unblinding up to Week 16.

Continuous variables (e.g., BASDAI change from baseline, etc.) will be analyzed using a mixed-effects model repeated measures (MMRM) which is valid under the missing at random (MAR) assumption. For analyses of these parameters, if all post-BSL values are missing then these missing values will not be imputed and this participant will be removed from the analysis

of the corresponding variable, i.e., it might be that the number of participants providing data to an analysis is smaller than the number of participants in the FAS.

For SI joint edema on MRI, a multiple imputation approach will be applied to handle missing data.

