2.4.1.1 Visit window

Analysis visit windows will be used for the data that is summarized by visit; they are based on the study visit and evaluation schedule and comprise a set of days around the nominal visit day. For any assessment, there are protocol defined scheduled visits around which analysis visit windows were created to cover the complete range of days within the study.

When visit windows are used, all visits will be re-aligned, i.e., they will be mapped into one of the visit windows. E.g., if the Week 4 visit of a subject is delayed and occurs on Day 46 instead of on Day 29, it will be re-aligned to visit window Week 8. In the case of major deviations from the visit schedule, or due to unscheduled visits, several assessments of a subject may fall in a particular visit window (either scheduled or unscheduled). Statistical approaches to handle multiple assessments in a given visit window are specified below.

As for the Week 60 (follow-up) visit, only assessments that come as nominal Week 60 visit will be directly assigned as Analysis Week 60 visit. Other assessments that are beyond the last on-treatment visit window (Week 52) won't be mapped to any analysis visit. Of note, subjects are allowed to have gaps in visits.

Table 2-1 Analysis visit windows

| Analysis visit | Target Day | Group 1 | Group 2 | Group 3 | Group 4 | Group 5 | Group 6 |
|----------------|------------|----------|----------|----------|----------|----------|----------|
| Baseline | 1 | ≤ 1 | ≤ 7 |
| Week 1 | 8 | 2-11 | 2-11 | | | | |
| Week 2 | 15 | 12-18 | 12-22 | | | | |
| Week 3 | 22 | 19-25 | | | | | |

| | | | | | | | |
|---------|-----|---------|---------|---------|---------|---------|---------|
| Week 4 | 29 | 26-43 | 23-57 | | | | |
| Week 8 | 57 | 44-71 | | 2-85 | 2-85 | | |
| Week 12 | 85 | 72-99 | 58-99 | | | | |
| Week 16 | 113 | 100-127 | 100-155 | 86-141 | 86-239 | 2-239 | 8-239 |
| Week 20 | 141 | 128-155 | | | | | |
| Week 24 | 169 | 156-183 | 156-169 | 142-225 | | | |
| Week 28 | 197 | 184-211 | 170-239 | | | | |
| Week 32 | 225 | 212-239 | | | | | |
| Week 36 | 253 | 240-267 | | | | | |
| Week 40 | 281 | 268-295 | 240-323 | 226-323 | | | |
| Week 44 | 309 | 296-323 | | | | | |
| Week 48 | 337 | 324-351 | | | | | |
| Week 52 | 365 | 352-379 | 324-379 | 268-379 | 240-435 | 240-379 | 240-435 |

*The first administration of randomized study treatment (first dose) is defined as Day 1.

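### An early end-of-treatment MRI falls in the Day 8-239 window, is labelled Week 16, and so blocks the imputation that the SI joint edema question calls for

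*SAP*

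**What the plan says.** For SI joint edema, SAP 2.6.1 asks about the "change from baseline in SI joint edema on MRI at Week 16 in Chinese participants with active nr-axSpA had participants completed 16 week-treatment". The other continuous endpoints have the same form, for example "change from baseline in BASDAI at Week 16 in Chinese participants with active nr-axSpA had patients completed 16 weeks-treatment". The estimand attribute reads "Intercurrent event: discontinuation from treatment or study prior to Week 16".

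SAP 2.6.3 then states that continuous variables "will be analyzed using a mixed-effects model repeated measures (MMRM) which is valid under the missing at random (MAR) assumption". For MRI, SAP 2.6.2 and 2.6.3 give an ANCOVA after multiple imputation of missing values. Binary variables have an explicit rule: participants who stop treatment or leave the study "will be considered as non-responders from the time of discontinuation through Week 16".

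SAP 2.4.1.1 says that "all visits will be re-aligned, i.e., they will be mapped into one of the visit windows", and extends this to unscheduled visits. The Week 16 row of Table 2-1, Groups 1 to 6 in order, is "100-127 | 100-155 | 86-141 | 86-239 | 2-239 | 8-239". MRI is Group 6. BASDAI, BASFI and hsCRP are in Group 1; SF-36 and ASQoL are in Group 3. For post-baseline efficacy, Table 2-2 picks the value nearest the target day. Its only treatment-related condition is the switch from placebo to secukinumab.

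Protocol Table 8-1 schedules MRI at screening, Week 16 and the end-of-treatment visit. Its footnote 2 places that last visit 4 weeks after the last dose for anyone who leaves the study early.

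**The concern.** Multiple imputation fits the MRI question, but it acts only on values that are missing. MRI has one post-baseline window before Week 52, so any scan from Day 8 to Day 239 is a candidate for Week 16. The end-of-treatment scan of an early leaver is therefore recorded as an observed Week 16 result, although it was taken after 1 to 6 of the 7 double-blind doses and weeks before the target day.

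At stake is what the MRI estimate means. For those participants an early, incomplete-treatment value stands in for the completed-treatment value that the plan intends to impute. The SAP does handle one visit by name: for the follow-up visit, "only assessments that come as nominal Week 60 visit will be directly assigned as Analysis Week 60 visit". It has no matching rule for an early end-of-treatment visit.

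**Working it through.** **1. Reproduce the MRI window.** SAP 2.4.1.1 sets the lower limit at the previous upper limit plus 1, and the upper limit at the target day plus the integer part of half the gap to the next target.
- Lower: the MRI baseline may extend to Day 7 (Tables 2-1 and 2-2), so 7 + 1 = 8.
- Upper: 113 + int((365 - 113)/2) = 113 + 126 = 239.

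This matches Day 8-239. The window is not a typing error. It reaches 113 - 8 = 105 days before the target and 239 - 113 = 126 days after it.

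**2. Place the early end-of-treatment scan.** Double-blind doses are at baseline and Weeks 1, 2, 3, 4, 8 and 12 (Protocol 6.1.3), seven in all. Dose day = 1 + 7 x week. Scan day = dose day + 28. Days early = 113 - scan day.

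**3. Map that visit with Table 2-1.** Group 1: Week 4 = 26-43, Week 8 = 44-71, Week 12 = 72-99, Week 16 = 100-127. Group 3: Week 8 = 2-85, Week 16 = 86-141. MRI: Week 16 = 8-239.

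| Last dose | Dose day | Scan day | Days early | MRI label | Group 1 label | Group 3 label |
|---|---|---|---|---|---|---|
| Baseline | 1 | 29 | 84 | Week 16 | Week 4 | Week 8 |
| Week 1 | 8 | 36 | 77 | Week 16 | Week 4 | Week 8 |
| Week 2 | 15 | 43 | 70 | Week 16 | Week 4 | Week 8 |
| Week 3 | 22 | 50 | 63 | Week 16 | Week 8 | Week 8 |
| Week 4 | 29 | 57 | 56 | Week 16 | Week 8 | Week 8 |
| Week 8 | 57 | 85 | 28 | Week 16 | Week 12 | Week 8 |
| Week 12 | 85 | 113 | 0 | Week 16 | Week 16 | Week 16 |

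For six of the seven possible last doses, the scan is early yet carries the Week 16 label. For Groups 1 and 3 the same visit never maps to Week 16 in those six cases, so Week 16 stays missing there and the MMRM handles it as intended. The count of six describes the windows; it is not a frequency of participants.

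**4. Condition.** The early scan is used only if no other scan lies closer to Day 113. A participant who has left the study has no later scheduled MRI before Day 239. One who stops treatment but stays in the study should return for the scheduled visits (Protocol 9.1.1), and a Week 16 scan would then be chosen instead.

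**The case against.** Four points can be made on the other side.

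*The target is already stated.* A reader might infer from the bare intercurrent-event attribute that the SAP has no strategy for the continuous endpoints. That does not hold. The hypothetical strategy is written into each clinical question, and MMRM under MAR and multiple imputation suit it. What remains open is only which observed values enter.

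*The group is narrow.* It needs someone who leaves the study early, still returns, has the MRI, and has no scan nearer Day 113. After withdrawal of consent, Protocol 9.1.2 provides for no further assessments. A scan on Day 85, after six of seven doses, may also differ little from a Week 16 value. This stands, and it limits the weight of the point.

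*A rule may exist out of sight.* Parts of the SAP, including Section 2.12 and text after the MRI definition in Section 5.1, are not visible, and the programming specifications are separate documents. This lowers certainty. But Table 2-1, Table 2-2 and Section 2.6.3 are visible, and applied as written they give the result above.

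*The MMRM endpoints.* A reader might infer that off-treatment values also distort BASDAI, BASFI, hsCRP, SF-36 PCS and ASQoL. The documents do not show this. That such values stay in the model is inferred from general mapping rules and is not stated. Protocol 9.1.1 sets the minimum data after stopping treatment at concomitant treatments and adverse events. This supports a request for clarification, not a finding of misalignment.

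**Conclusion.** The MRI point holds as a minor one. Rules stated in the SAP, taken together, label a scan on Day 29 to 85 as Week 16 and prevent the imputation that the MRI question calls for. The error in timing is 28 to 84 days per affected scan.

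This assumes that the participant attends the end-of-treatment visit about 4 weeks after the last dose, that the MRI is done, that no closer scan exists, and that no rule outside the visible text overrides the window.

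The documents give no rates for stopping, returning or scan completion, so the number of affected values cannot be determined; it is probably small. A reader might infer that the MRI treatment effect is materially diluted. The documents support neither a size nor a direction for such an effect. The primary ASAS40 analysis has its own discontinuation rule (SAP 2.5.3) and is unaffected, and the study estimates rather than tests (SAP 3.1).

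**What to change.** **MRI.** In SAP 2.4.1.1 or 2.6.3, state that an end-of-treatment MRI in a participant who stopped before the Week 12 dose is not labelled Week 16, and that the Week 16 value is multiply imputed. Allow the early scan as an intermediate variable in the imputation model; the template in SAP 5.5.1.2.1 already foresees including all data collection visits. Its gain may be limited, because participants who complete Week 16 have no scheduled MRI between screening and that visit from which to estimate the relation.

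**Secondary clarification.** In SAP 2.6.3, state whether values observed after permanent treatment discontinuation are set to missing before the MMRM or the multiple imputation. Count from the time of discontinuation, as the binary rule does. A limit of 28 days after the last dose would not do: the early MRI falls exactly 28 days after the last dose and would be kept, and after a last dose on Day 1 it would also keep values on Days 15, 22 and 29 although the Week 1 to 3 doses were missed. If a section not visible here already has the rule, a cross-reference is enough.

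**Cost.** A sentence or two and one derivation flag, with slightly fewer observed MRI values and more reliance on MAR.

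**Timing.** Amendment 2 is dated before the Week 52 lock, and Protocol Table 6-3 allows statisticians to be unblinded at the primary endpoint analysis. If the Week 16 analysis has already been run unblinded, do not replace it: document the rule that was used and present the alternative as a supplementary analysis labelled post hoc.

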2.7 Safety analyses

The analysis of safety data by treatment may be provided for each Treatment Period separately and all periods combined, as appropriate. The analysis of safety data will be conducted on the Safety Set, which includes subjects who receive any study treatment. Safety analysis will be performed on treatment received or actual treatment as described below:

The actual treatment or treatment received for summaries of safety data will differ to the treatment assigned at randomization only if a subject received the wrong treatment during the entire study.

For those subjects who received not the treatment assigned at randomization, i.e. who received erroneously the wrong treatment at least once, an additional AE listing will be prepared displaying which events occurred after the treatment errors.

The safety variables to be analyzed include Adverse events (AEs), clinical laboratory tests (hematology, chemistry and urinalysis), physical examination results, ECGs, and deaths. Safety variables are to be tabulated by descriptive statistics (n, mean, median, standard deviation, minimum, and maximum; or n and percent). No formal statistical testing is planned.

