Study treatment	Secukinumab 150 mg s.c. and matching placebo
Treatment of interest	The randomized treatment (either secukinumab or placebo up to Week 16 and secukinumab after Week 16) with or without the allowed concomitant medication for managing axSpA inflammatory back pain (add-on to standard of care). The dose of the allowed concomitant medication must remain stable during the trial and allowed to modify only after Week 24.
Efficacy assessments	

• Assessment of SpondyloArthritis International Society criteria (ASAS)

• patient's global assessment of disease activity (VAS)

• patient's assessment of back pain intensity (VAS)

• Bath Ankylosing Spondylitis Functional Index (BASFI)

• Bath Ankylosing Spondylitis Disease Activity Index (BASDAI)

 

Key safety assessments	

• QuantiFERON TB-Gold test or PPD skin test

• Chest X-ray or CT

• Physical examination

• Vital signs

• Height and weight

• Laboratory evaluations [REDACTED]

• Electrocardiogram

• Pregnancy and assessment of fertility

• Local tolerability (Injection site reactions)

• Tolerability of secukinumab

Other assessments	

• Health-related Quality of Life

• SF-36

• ASQoL

[REDACTED]

• HLA-B27

[REDACTED]

• X-Ray of the sacroiliac joints

[REDACTED]

Data analysis	The primary analysis will be conducted via logistic regression with treatment and stratification factor (CRP+/MRI+, CRP+/MRI-, CRP-/MRI+) as factors and weight as a covariate. Difference in response proportions between secukinumab regimen and placebo regimen and the corresponding 95% confidence interval (CI) will be computed utilizing the logistic regression model fitted.
Key words	Non-radiographic spondyloarthritis, chronic inflammatory disease, inflammatory back pain, secukinumab, AIN457

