### **6.1.3 Treatment arms/group**

#### **Double Blind Period (Treatment Period 1)**

Participants in double-blind period will be assigned to one of the following two treatment groups in a ratio of 1:1. Participants will receive study treatment at BSL, Weeks 1, 2, 3, and 4, followed by treatment every 4 weeks through Week 12.

- Group 1: secukinumab 150 mg (1 mL, 150 mg/mL) s.c. PFS at BSL, Weeks 1, 2, and 3, followed by administration every 4 weeks starting at Week 4.
- Group 2: placebo (1 mL) s.c. PFS at BSL, Weeks 1, 2 and 3, followed by administration every 4 weeks starting at Week 4.

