#### **Open Label Period (Treatment Period 2 and 3)**

**Treatment Period 2:** At Week 16, Group 1 participants will continue using secukinumab 150 mg and Group 2 participants will start receiving secukinumab 150 mg dosing every four weeks. Treatment will be provided open label from Week 16 onward, as all participants will be taking 150 mg s.c. every 4 weeks. However, all participants and investigators/site staff will remain blinded to the original randomized treatment group assignment (150 mg vs placebo).

**Treatment Period 3:** At Week 24, participants in open label period will be assessed as being Open Label Period Responder or Open Label Period non-responder and will receive the study treatment every 4 weeks through Week 48 as follows.

- **Open Label Period Responder:** Secukinumab 150 mg provided in a 1 mL PFS (**one** PFS for 150 mg dose, s.c.), administration every 4 weeks starting at Week 24.
- **Open Label Period non-responder:** Secukinumab 150 mg provided in a 1 mL PFS (**two** PFS for 300 mg dose, s.c.), administration every 4 weeks starting at Week 24.

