1.1 Study design

This is a randomized, double-blind, placebo-controlled study of secukinumab 150 mg s.c. to evaluate the safety, tolerability, and efficacy in Chinese participants with active non-radiographic axial spondyloarthritis (nr-axSpA).

A screening period of up to 10 weeks before randomization will assess participant eligibility, followed by 16 weeks of double-blind treatment period and 44 weeks open label period.

Approximately 134 participants will be randomized in a ratio of 1:1 to receive secukinumab 150 mg s.c. or placebo:

- Group 1: secukinumab 150 mg (1mL, 150 mg/mL) s.c. pre-filled syringe (PFS) at baseline (BSL), Weeks 1, 2, and 3, followed by administration every four weeks starting at Week 4
- Group 2: placebo (1 mL) s.c. PFS at BSL, Week 1, 2 and 3, followed by administration every four weeks starting at Week 4

Participants will be stratified at randomization according to the subgroup of objective sign of inflammation they belong to (based on their CRP and MRI status at screening: CRP+ and MRI+, CRP+ and MRI-, CRP- and MRI+).

Additionally, it is planned to enroll no more than approximately 10% Tumor Necrosis Factor – Inadequate Response (TNF α -IR) participants in the study.

The primary analysis will be performed after all participants complete Week 16 visit to support registration in China.

From Week 16, all participants will switch to open label secukinumab 150 mg s.c., including all placebo participants. The first dose of open label secukinumab 150 mg s.c. should start at the Week 16 visit, only after performing all assessments for that visit. However, all participants and investigators/site staff will remain blinded to the original randomized treatment group assignment (150 mg vs placebo).

At Week 24, non-responders (defined as not achieving ASAS20) will be escalated to secukinumab 300 mg s.c. Responders will continue secukinumab 150 mg s.c. treatment.

Study treatment will continue up to Week 48.

At end of treatment visit will be performed 4 weeks after last study treatment administration i.e. at Week 52 and a post treatment follow-up visit is to be done 12 weeks after last study treatment administration for all participants (regardless of whether they complete the entire study as planned or exit the study early).

A primary endpoint analysis will be conducted after all participants complete Week 16 visit. The final analysis will be conducted on all participant data at the time the study ends.

[figure not shown]

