2.2 Analysis sets

The following analysis sets will be used in this study:

Randomized set: The randomized set will be defined as all participants who were randomized. Unless otherwise specified, mis-randomized participants (mis-randomized in IRT) will be excluded from the randomized set.

Mis-randomized participants are defined as those participants who were mistakenly randomized into the IRT prior to the site confirming all eligibility criteria had been met and to whom no study medication was given. Mis-randomized participants are treated as screen failures.

Full analysis set (FAS): The FAS will be comprised of all participants from the randomized set to whom study treatment has been assigned. Following the intent-to-treat principle, participants will be evaluated according to the treatment assigned to at randomization, but actual stratum, if stratified randomization is used.

Safety set: The safety set includes all participants who took at least one dose of study treatment during the treatment period. participants will be evaluated according to treatment received.

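### SAP 2.7's entire-study condition leaves a participant given placebo instead of secukinumab at every blinded dose, then the planned Week 16 dose, in the secukinumab safety column

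*SAP*

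**What the plan says.** The Safety Set in SAP 2.2 is as-treated: "participants will be evaluated according to treatment received". Protocol 12.1 says the same, and neither adds a condition on how long the wrong treatment lasted.

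SAP 2.7 then states how this is applied: "Safety analysis will be performed on treatment received or actual treatment as described below". The description that follows lets the actual treatment differ from the randomized one "only if a subject received the wrong treatment during the entire study". Anyone given the wrong treatment at least once gets an additional adverse-event listing of what happened after the error. No change to the tables is described for such participants.

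On the design, SAP 1.1 says: "From Week 16, all participants will switch to open label secukinumab 150 mg s.c., including all placebo participants". Protocol 6.1.3 gives the Week 16 step by arm: "Group 1 participants will continue using secukinumab 150 mg and Group 2 participants will start receiving secukinumab 150 mg dosing every four weeks".

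**The concern.** An entire-study condition suits a design in which the arms stay different to the end. Here they become the same at Week 16. Once the planned open-label dose is given, a participant has received at least one correct dose, whatever happened before. The condition can then fail for exactly the participant it should catch: one who received the other arm's drug throughout the blinded period.

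Day 1 to Week 16 is the only placebo-controlled safety comparison in the trial. At stake is whether its two columns hold the people who took each treatment, as the Safety Set definition promises.

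**Working it through.** The documents give no figure on this point, so there is none to reproduce. The check is a dose count followed by a reading of the rule.

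**Inputs**
- Blinded doses, protocol 6.1.3: "Participants will receive study treatment at BSL, Weeks 1, 2, 3, and 4, followed by treatment every 4 weeks through Week 12". That is baseline and Weeks 1, 2, 3, 4, 8 and 12, or 7 doses.
- Open-label doses: every four weeks from Week 16, and SAP 1.1 says "Study treatment will continue up to Week 48". That is (48 − 16)/4 + 1 = 9 doses, and 7 + 9 = 16 in all.
- Planned treatment from Week 16: secukinumab in both arms.
- Planned size: about 134 randomized 1:1, or 134/2 = 67 per arm.

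**Applying the rule.** Suppose a participant receives the other arm's drug at all 7 blinded visits and the planned drug from Week 16. Two readings of the rule are possible. The regimen reading compares each dose with the dose planned for that arm at that visit. The label reading asks only whether the participant ever received the drug named by the randomized arm.

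| Randomized to | Given when blinded | Last dose | Wrong doses | Regimen reading | Label reading |
|---|---|---|---|---|---|
| Secukinumab | Placebo | Week 12 | 7 of 7 | reassigned | reassigned |
| Secukinumab | Placebo | Week 16 | 7 of 8 | not reassigned | not reassigned |
| Secukinumab | Placebo | Week 48 | 7 of 16 (44%) | not reassigned | not reassigned |
| Placebo | Secukinumab | Week 12 | 7 of 7 | reassigned | reassigned |
| Placebo | Secukinumab | Week 16 | 7 of 8 | not reassigned | reassigned |
| Placebo | Secukinumab | Week 48 | 7 of 16 (44%) | not reassigned | reassigned |

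For the secukinumab-randomized participant, both readings fail once the open-label dose is given. For the placebo-randomized participant, the readings disagree.

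**Could the phrase mean the period being analysed?** SAP 2.1.1.1 lists Week 1 to Week 16 and the entire study side by side as two different safety periods. The SAP's own usage is against that reading.

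**Size in the Day 1 to Week 16 tables.** One participant is 1/67 = 1.5% of an arm. Let x of 67 in the secukinumab column have an event, including the misplaced participant. Moving that participant out changes the rate from x/67 to (x − 1)/66, a fall of (67 − x)/(67 × 66). This is largest at x = 1, where it is 1/67 = 1.5 points.

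**Knock-on.** One route to common-event status in SAP Table 2-3 is 2% of the secukinumab arm up to Week 16. That is 0.02 × 67 = 1.34, so two participants are needed, and one misplaced case can decide whether a preferred term qualifies by that route.

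**Exposure.** Table 2-3 plans exposure-adjusted rates only for the entire treatment period. SAP 2.4.1 splits exposure at the treatment switch, so up to 16 weeks of one participant's exposure would sit in the wrong column of those tables.

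**The case against.** Several points on the other side have force.

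- **The rule still works for some participants.** A reader might infer that it can never apply to anyone who reaches Week 16. That goes too far. Someone wrongly dosed at every blinded visit who attends Week 16 but has stopped treatment has received only wrong treatment, and the rule applies. What blocks it is the planned open-label dose, not attendance.
- **The placebo-to-active case is arguable.** A reader might take a placebo-randomized participant given secukinumab throughout as the plain example. SAP 2.1.1.1 lists the randomized treatments as two labels, and on those labels this participant never received placebo and could be reassigned. Against that, the treatment-of-interest row of the protocol summary describes the randomized treatment as a regimen that includes secukinumab after Week 16. That row is not a safety-analysis definition, so the case stays ambiguous.
- **Period-specific grouping is partly foreseen.** SAP 2.1 says a participant's treatment group may depend on the analysis period and on whether efficacy or safety is assessed. SAP 2.7 allows safety to be shown by treatment period. Neither remark gives a test for actual treatment, and neither overrides the word only in the rule.
- **SAP 2.7 may simply define the Safety Set's term.** It does present itself as the description of treatment received. The result is still that someone who took only placebo while blinded is tabulated as secukinumab, which does not fit SAP 2.2 or protocol 12.1.
- **Exposure does not touch the blinded comparison.** A reader might infer that misplaced exposure distorts the Day 1 to Week 16 incidences. It cannot, because only crude incidence is planned for that period.
- **The consequence is small.** IRT supplies the kit number at each administration (protocol 6.6.1), and dosing is normally on site (protocol 6.7.2). Safety is descriptive with no formal testing, and the listing makes any error visible. The primary efficacy analysis follows assigned treatment and is unaffected. All of this stands and limits the severity.

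**Conclusion.** The rule is wrong as written for one situation and unclear for another. It is wrong for a secukinumab-randomized participant given placebo at all blinded doses and then the planned Week 16 dose: the participant stays in the secukinumab column on either reading. It is unclear for the reverse error.

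The effect is up to 1.5 points on one arm's crude incidence per participant at the planned 67 per arm, plus up to 16 weeks of misplaced exposure in the entire-period tables. Both figures assume that a whole-period error has occurred. The documents give no error rate, and nothing in them suggests that such an error is likely. The documents therefore do not support a conclusion that the safety tables are wrong. They show only that the rule would give a wrong entry if the error arose. Severity is minor.

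**What to change.** In SAP 2.7, define actual treatment by analysis period. For the double-blind period, let it differ from randomized treatment when the wrong treatment was received at all doses given from baseline to Week 12, whatever was given from Week 16. This classifies the participant as treated in both directions (7 of 7 blinded doses wrong) and also covers those who stop early. Use the same classification when assigning exposure in the entire-period exposure-adjusted tables, so that incidence and exposure follow one rule. Keep the existing listing for partial errors, and say that these participants stay in their randomized column. This reconciles SAP 2.7 with SAP 2.2 and protocol 12.1.

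The cost is a sentence or two in the SAP and a small change to one derivation. No new data are needed: kit numbers come from IRT, and protocol Table 10-1 already sends treatment errors to the dosing CRF. If no whole-period error occurred, one line in the study report closes the point.
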